2.4.3 Extent of investigational medicinal product exposure and compliance

The extent of IMP exposure and compliance will be assessed and summarized by actual treatment within the safety population ([Section 2.3.2](#)).

2.4.3.1 Extent of investigational medicinal product exposure

The extent of IMP exposure will be assessed by the duration of IMP exposure.

Duration of IMP exposure in weeks is defined as (last dose date + 7 - first dose date)/7 days, regardless of unplanned intermittent discontinuations (see [Section 2.5.3](#) for calculation in case of missing or incomplete data).

Duration of IMP exposure will be summarized descriptively as a quantitative variable (number, mean, SD, median, minimum, and maximum) expressed in weeks. In addition, duration of treatment exposure will also be summarized categorically by numbers and percentages for each of

the following categories and cumulatively according to these categories: ≥ 1 day and <2 weeks, ≥ 2 weeks and <4 weeks, ≥ 4 weeks and <6 weeks, ≥ 6 weeks and <12 weeks, ≥ 12 weeks and <16 weeks, ≥ 16 weeks and <20 weeks, ≥ 20 weeks and <24 weeks, ≥ 24 weeks and <36 weeks. Non-integer values will be rounded to 1 decimal place.

Additionally, the cumulative duration of treatment exposure will be provided, defined as the sum of the duration of treatment exposure for all patients, and will be expressed in patient-years.

2.4.3.2 Compliance

A given administration will be considered non-compliant if the patient did not take the planned dose of treatment as required by the protocol. No imputation will be made for patients with missing or incomplete data.

Overall percentage of compliance for a patient will be defined as $100 - (\% \text{ days with below-planned dosing} + \% \text{ days with above-planned dosing})$, considering that injections should be performed every week ± 2 days as per protocol.

Above-planned dosing percentage for a patient will be defined as $100 * \text{the number of days with more than 1 injection administration within the 5 days before divided by the duration of IMP injection exposure in days}$.

Below-planned dosing percentage for a patient will be defined as $100 * \text{the number of days with no injection administration within the previous 9 days divided by the duration of IMP injection exposure in days}$.

Treatment compliance, above-planned, and under-planned dosing percentages will be summarized descriptively as quantitative variables (number, mean, SD, median, minimum, and maximum). The percentage of patients whose compliance is $<80\%$ will be summarized. In addition, numbers and percentages of patients with $[0;5]$, $]5;10]$, $]10;20]$, and $>20\%$ of days with above or under-planned dosing will also be provided.

In addition, the following parameters will be summarized by treatment arm:

- The number of advanced injections (≤ 3 days apart from the previous injection, 4 days apart from the previous injection) and the number of delayed injections (more than 9 days between two consecutive injections).
- The number of patients with at least one advanced injection and the number of patients with at least one delayed injection. A patient could be counted in several categories.
- The frequency of IMP injections (mean (SD), median, Min:Max description) will be defined for each patient as the average number of days between two consecutive injections: $(\text{last injection date} - \text{first injection date}) / (\text{number of injections} - 1)$ for patients with at least 2 injections.

Cases of overdose are reported in the AE e-CRF pages as AESI if symptomatic or AE if asymptomatic. The reported cases of overdose will be described in the AE analysis (see [Section 2.1.5](#) and [Section 2.4.5.1](#)).

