8.1.4 Route and method of administration

The route and method of administration are SC in the abdomen. SC injection sites should be alternated between the 4 quadrants of the abdomen (avoiding navel and waist areas) so that the same site is not injected for two consecutive weeks. The exact site of each injection will be documented on the source document. It is recommended that the injection occur at a site free of SSc involvement, if possible.

The IMP is administered every 7 days ± 2 days from initial IMP administration. This window is permitted per protocol to accommodate various circumstances (eg, pending laboratory results, management of AE, visit scheduling difficulty). The IMP administration should be performed by other site personnel, blinded from the person in charge of the preparation of the solutions and syringes.

If IMP administration is missed or temporarily discontinued, the initial schedule of injections may be resumed upon the investigator's medical judgment and discretion while the missed dose(s) will not be administered. This does not apply to permanent treatment discontinuation.

On days when the patient has a study visit, the IMP will be administered by the Investigator or delegate after clinic procedures and blood collection.

For doses not administered at the study site, the IMP will be administered by qualified site personnel and /or healthcare professionals (eg, visiting nurse service).

Patients should be monitored by site personnel/visiting nurse for at least 30 minutes or up to 2 hours as per country specific requirements after each administration for potential signs and symptoms that may suggest a hypersensitivity reaction.

For doses not given at the study site, a booklet will be provided to the patient to record information related to the injections; this booklet will be completed by the visiting nurse after each injection and will be kept as source data in the patient's study file. Patients will be instructed to bring the booklet back at the subsequent site visit for Investigator's review.

Between the protocol-scheduled on-site visits, interim visits to the site may be required for IMP dispensing. As an alternative to these visits, the IMP may be supplied from the site to the patient via a Sponsor-approved courier company where allowed by local regulations and approved by the patient.

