11.4.1.2 Compliance

A given administration will be considered noncompliant if the patient did not take the planned dose of treatment as required by the protocol. No imputation will be made for patients with missing or incomplete data.

Treatment compliance, above-planned and under-planned dosing percentages will be summarized descriptively (N, Mean, SD, Median, Min, and Max). The percentage of patients with compliance <80% will be summarized. In addition, number and percentage of patients with at least 1 above-planned dosing administration will be given, as well as the number and percentage of patients with 0, (0, 20%), and >20% under-planned dosing administrations.

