2.5 DATA HANDLING CONVENTIONS

2.5.1 General conventions

The following formulas will be used for computation of parameters.

Study day

Study day = assessment date - first IMP injection date + 1 (if assessment date \geq first IMP injection date), otherwise study day = assessment date - first IMP injection date, the day of first IMP injection being Day 1. For randomized but not treated patients, Day 1 is the day of randomization.

Demographic formulas

Age (years) = (date of informed consent - date of birth)/365.25

Renal function formulas

Creatinine clearance value will be derived using the equation of Cockcroft and Gault:

For male:

$$CL_{CR} \text{ (mL/min)} = \frac{(140 - age(\text{years})) * weight(\text{kg})}{0.814 * serumcreatinine(\mu\text{mol/L})}$$

For Female: result above multiplied by 0.85.

Date of last dose of investigational medicinal product

The date of the last dose of IMP is equal to the last date of administration reported on the IMP administration case report form page, or missing if the last administration date is unknown.

Lipids variables, laboratory safety variables, hs-CRP

For data below the lower limit of quantification (LLOQ)/limit of linearity, half of the lower limit value (ie, LLOQ/2) will be used for quantitative analyses. For data above the upper limit of quantification (ULOQ) / limit of linearity, the upper limit value (ie, ULOQ) will be used for quantitative analyses.

For ANCA parameter: values “<1:20” are considered as negative; other results are considered as positive.

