2.5.3 Missing data

For categorical variables, patients with missing data are not included in calculations of percentages unless otherwise specified. When relevant, the number of patients with missing data is presented.

Handling of computation of treatment duration if investigational medicinal product end of treatment date is missing

For the calculation of the treatment duration, the date of the last dose of IMP is equal to the date of last administration reported on the end-of-treatment case report form page. If this date is missing, the exposure duration should be left as missing.

The last dose intake should be clearly identified in the case report form and should not be approximated by the last returned package date.

Handling of medication missing/partial dates

No imputation of medication start/end dates or times will be performed. If a medication date or time is missing or partially missing and it cannot be determined whether it was taken prior or concomitantly, it will be considered as prior, concomitant, and post-treatment medication.

Handling of adverse events with missing or partial date/time of onset

Missing or partial adverse event onset dates and times will be imputed so that if the partial adverse event onset date/time information does not indicate that the adverse event started prior to treatment or after the treatment-emergent adverse event period, the adverse event will be classified as treatment-emergent. No imputation of adverse event end dates/times will be performed. These data imputations are for categorization purpose only and will not be used in listings. No imputation is planned for date/time of adverse event resolution.

Handling of adverse events when date and time of first investigational medicinal product administration is missing

When the date and time of the first IMP administration is missing, all adverse events that occurred on or after the day of randomization should be considered as treatment-emergent adverse events. The exposure duration should be kept as missing.

The last dose intake should be clearly identified in the case report form and should not be approximated by the last returned package date.

Handling of missing assessment of relationship of adverse events to investigational medicinal product

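### The SAP scores compliance in days beyond a 9-day gap although it defines non-compliance per administration, so patients who singly miss 5 or 6 of 24 doses are not counted as below 80% compliant

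*SAP*

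**What the plan says.** **Unit.** Protocol 11.4.1.2 states: "A given administration will be considered noncompliant if the patient did not take the planned dose of treatment as required by the protocol". It summarises under-planned and above-planned dosing in administrations, with an under-planned category above 20%, and asks for the percentage of patients below 80% compliance. It gives no formula. SAP 2.4.3.2 opens with nearly the same sentence.

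**Formula.** SAP 2.4.3.2 then sets overall compliance at 100 minus the percentages of days with below-planned and above-planned dosing. Below-planned is 100 times "the number of days with no injection administration within the previous 9 days divided by the duration of IMP injection exposure in days". Above-planned uses the "number of days with more than 1 injection administration within the 5 days before", over the same denominator. The planned output includes "The percentage of patients whose compliance is" under 80%, and bands of days with the top band above 20%.

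**Denominator.** Exposure (SAP 2.4.3.1) is ("last dose date + 7 - first dose date)/7 days", that is, last dose minus first dose plus 7 when expressed in days.

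**Last dose date.** SAP 2.5.1: "The date of the last dose of IMP is equal to the last date of administration reported on the IMP administration case report form page". SAP 2.5.3, on computing how long a patient was treated, says: "the date of the last dose of IMP is equal to the date of last administration reported on the end-of-treatment case report form page". Where no such date was recorded, exposure is left missing.

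**Window.** Protocol 8.1.4: "The IMP is administered every 7 days ± 2 days from initial IMP administration". SAP 2.4.3.2 cites a weekly ± 2 day schedule as per protocol and applies it to the gap between consecutive injections. Gaps of 3 days or less, or of 4 days, are advanced; gaps over 9 days are delayed.

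**The concern.** The section changes its unit partway through. Someone reading the below-80% figure will take it as the share of patients who received less than 80% of their injections, because both documents introduce compliance that way. The formula measures something else. It forgives the first 9 days of every gap, so an omitted weekly dose costs less than the week it leaves uncovered, and the shortfall recurs with each separate miss.

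The primary estimand is treatment policy and uses data regardless of adherence. In a proof-of-concept trial, a null result would naturally lead a reader to the compliance table to ask whether patients were under-dosed. A cut-off that overlooks patients who took three quarters of their doses makes that table less informative than it appears.

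Two smaller inconsistencies sit beside this one: two CRF pages are named as the source of the last dose date, which drives the denominator, and the SAP's between-injection limits may not match the protocol's dosing window.

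**Working it through.** **Inputs.** Weekly dosing from Day 1 with the last dose at Week 23 (Protocol flow chart) gives 24 planned doses, 161 days from first to last.

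**Exposure first.** (161 + 7)/7 = 24.0 weeks = 168 days, which agrees with the stated 24 weeks of treatment. Perfect weekly dosing scores 100%.

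**Cost of one gap.** For a gap of *g* days between injections, the below-planned days number *g* − 10 if the current day belongs to the 9-day window, and *g* − 9 if it does not. A single missed dose gives *g* = 14, so 4 or 5 days.

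**Isolated misses.** Score = 100 − 100 × (4*m* or 5*m*)/168. Dose basis = 100 × (24 − *m*)/24.

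| Missed, *m* | Doses taken | SAP score, current day counted | SAP score, not counted |
|---|---|---|---|
| 4 | 83.3% | 90.5% | 88.1% |
| 5 | 79.2% | 88.1% | 85.1% |
| 6 | 75.0% | 85.7% | 82.1% |
| 7 | 70.8% | 83.3% | 79.2% |
| 8 | 66.7% | 81.0% | 76.2% |
| 9 | 62.5% | 78.6% | 73.2% |

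A dose basis crosses 80% at 5 misses. The SAP formula crosses at 9 or 7.

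The banded output shifts too. Six isolated misses are 6/24 = 25% of administrations, in the protocol's category above 20%. In days they are 24/168 = 14.3% or 30/168 = 17.9%, in the SAP's band from 10 to 20%.

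**Clustered misses, still 18 of 24 doses taken** (current day counted / not counted):

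- Three pairs (21-day gaps): 33 or 36 days, 80.4% / 78.6%.
- Two runs of three (28-day gaps): 36 or 38 days, 78.6% / 77.4%.
- Last six doses not given: exposure shrinks to 126 days, 100% / 100%.

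Over all 100,947 ways of missing 6 doses with the first dose taken, 99.3% / 69.0% score at least 80%. This counts patterns equally; it is not a forecast of patient behaviour.

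**Dosing window.** If Protocol 8.1.4 anchors every dose to the first, consecutive gaps of 3 to 11 days are permitted (7 − 4 to 7 + 4). The SAP deducts days for some of these and counts them as advanced or delayed. With timing drawn uniformly within ± 2 days (an assumption), mean scores run from 92.6% to 97.4% across the readings of the 9-day and 5-day windows, and no simulated patient falls below 80%. The share of such patients with at least one advanced or delayed injection is about 27% if 80% of doses fall on the exact day, 71% if 60% do, and over 99% if timing is uniform. In the first two cases the remaining doses are assumed to be spread evenly over the other four days. If 8.1.4 instead means an interval of 5 to 9 days, the SAP's limits agree with it and this conflict disappears.

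**The case against.** **A reader might infer that anyone missing 6 of 24 doses scores above 80%.** That is not so. Two runs of three fall below 80% under both readings, and three pairs straddle the line. The statement holds for isolated misses, and for most but not all patterns.

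**A reader might infer that patients who dose within the protocol window are labelled non-compliant.** The documents do not support this. Under an anchored window such patients can lose days from the score and appear in the advanced or delayed counts, but the SAP reports those counts separately and does not call them non-compliance. Falling below 80% takes an extreme pattern, alternating 2 days early and 2 days late throughout; that scores 66.3% to 80.6% depending on the reading, so some readings do not flag even this patient. The wording of 8.1.4 also admits the interval reading.

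**A reader might infer that patients lost to follow-up drop out of the compliance table.** The two sources for the last dose date do conflict. Whether any patient is affected is unknown: the CRF is not among the documents, and the protocol asks for a premature end-of-treatment visit after early discontinuation.

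**The strongest argument against acting** is that little depends on the figure. Compliance defines no analysis set, the on-treatment analysis uses last injection plus 7 days, and missed doses show elsewhere: a patient with six isolated misses has six delayed injections and a mean interval of 161/17 = 9.47 days. This argument stands as a limit on importance. It does not reconcile the per-administration definition with the per-day formula.

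**Conclusion.** The point holds. The SAP's compliance percentage is not in the unit that the SAP and protocol define, and for isolated missed doses it is lenient at the planned 80% cut-off. Patients who took 79.2% or 75.0% of doses score 85.1% to 88.1% or 82.1% to 85.7%. The flag needs 7 or 9 isolated misses instead of 5. The ranges come entirely from the unstated treatment of the current day.

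These figures assume otherwise exact weekly dosing, a final dose at Week 23 and no above-planned days. Clustered misses may be caught.

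The conflict over the last dose date is real but of unknown effect. The mismatch with the protocol's dosing window is conditional on how 8.1.4 is read. What is affected is a descriptive summary on the safety population; the primary analysis does not change.

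**What to change.** 1. In SAP 2.4.3.2, define compliance as 100 × planned injections given / planned injections over the exposure period. Define under-planned dosing as the percentage of planned administrations not given, using the unit of Protocol 11.4.1.2, and express above-planned dosing in administrations too. Eighteen of 24 doses then scores 75.0% for any pattern in which the first and last planned doses are given.
2. State that this measure counts planned doses only over the exposure period, so it does not detect early stopping (18 of 18 is still 100%). Report early stopping through exposure duration, which SAP 2.4.3.1 already tabulates.
3. Use one source for the last dose date in SAP 2.5.1 and 2.5.3: the last dated injection on the IMP administration page, with the end-of-treatment page as fallback.
4. Reconcile the between-injection limits for advanced and delayed injections with Protocol 8.1.4. Which window applies is for the sponsor to settle.
5. If any day-based measure is kept, state whether the current day belongs to the 9-day and 5-day windows.

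The cost is SAP wording and simpler programming, with no new data. Reported compliance may look slightly less favourable.

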2.4.4 Analyses of efficacy endpoints

All efficacy measurements, scheduled or unscheduled, will be assigned to time points according to analysis windows as defined in [Table 3](#).

All endpoints will be described at each visit on the ITT population.

2.4.4.1 Analysis of primary efficacy endpoint(s)

2.4.4.1.1 Primary efficacy analysis

The primary estimand will be the difference in mean change from baseline to 24 weeks in mRSS in all randomized patients, regardless of whether or not patients completed the treatment period. This estimand corresponds to a “treatment policy strategy”.

A spaghetti plot presentation of individual data by treatment group will be presented.

The change in mRSS from baseline to Week 24 will be analyzed in the ITT population using a MMRM approach. All post-baseline data available from Week 4 to Week 24 analysis windows will be included in the analysis, regardless of adherence to treatment. The lower the mRSS is, the better it is for the patient.

Missing data will be accounted for by the MMRM. The model includes the fixed categorical effects of treatment group (placebo, SAR156597), randomization strata (as per IRT, SSc-ILD: Yes/No), time point (Week 4, Week 8, Week 12, Week 24 as defined in [Section 2.5.4](#)), randomization strata-by-time point interaction and treatment-by-time point interaction, as well as the continuous fixed covariates of baseline mRSS value and baseline value-by-time point interaction.

This model will be run using SAS Mixed procedure. The repeated-measures analysis will be based on the restricted maximum likelihood method (Newton-Raphson algorithm) assuming an unstructured correlation matrix to model the within-patient errors. Denominator degrees of freedom will be estimated using Kenward-Roger approximation. This model will provide baseline adjusted LSmeans estimates at Week 24 for both treatment groups with their corresponding standard errors (SEs) and 95% confidence intervals (CIs). To compare SAR156597 to the placebo group, an appropriate contrast statement will be used to test the difference of these estimates at the 5% one-sided alpha level. The 95% and 90% confidence intervals of the difference will be provided. Let μ_0 and μ_1 be the population means of the change from baseline in mRSS at Week 24 under placebo and SAR156597, respectively. The null hypothesis that will be tested is “ $H_0: \mu_0 = \mu_1$ ” versus “ $H_1: \mu_0 > \mu_1$ ”.

The MMRM model relies on the “missing-at-random” (MAR) assumption. As we can never exclude the possibility for a not-missing-at-random (NMAR) missingness mechanism, if more than 5 patients have no value for mRSS data at Week 24, a sensitivity analysis to explore the impact of non-ignorable missingness on the primary efficacy analysis will be conducted (see control-based pattern imputation model defined in [Section 2.4.4.1.7](#)).

2.4.4.1.2 Analysis of residuals

The analysis of the residuals of the MMRM will be primarily based on studentized residuals. The studentized residuals will be presented graphically using histogram and QQ-plot.

2.4.4.1.3 On-treatment analysis

A secondary estimand will be the difference in mean change from baseline to 24 weeks in mRSS estimated during the on-treatment period (from the first administration of the IMP to the last administration of the IMP + 7 days). This estimand corresponds to a “while on treatment strategy”. This estimand will be considered for describing the effect of treatment as long as patients adhere to their randomized treatment.

As a secondary analysis, the change in mRSS from baseline to Week 24 will also be analyzed in the randomized and treated population using the same MMRM model as described above, including only post-baseline data measured during the on-treatment period (from the first administration of the IMP to the last administration of the IMP + 7 days), analyzed according to the treatment group allocated by randomization.

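### The secondary mRSS estimand is labelled while-on-treatment, but for patients who stop before the Week 24 window its MMRM essentially targets the effect of continued treatment (minor, secondary analysis only)

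*SAP*

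**What the plan says.** **Primary analysis (SAP 2.4.4.1.1).** Of the primary estimand the SAP says: "This estimand corresponds to a “treatment policy strategy". All values from the Week 4 to Week 24 windows are used, on or off treatment. On gaps in the data: "Missing data will be accounted for by the MMRM". The section adds: "The MMRM model relies on the “missing-at-random” (MAR) assumption".

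**Secondary estimand (SAP 2.4.4.1.3).** The label sentence reads: "This estimand corresponds to a “while on treatment strategy". The explanation is: "This estimand will be considered for describing the effect of treatment as long as patients adhere to their randomized treatment". For the analysis, "the change in mRSS from baseline to Week 24 will also be analyzed in the randomized and treated population using the same MMRM model", "including only post-baseline data measured during the on-treatment period". That period ends 7 days after the last dose, and patients are analysed in their allocated group. No other outcome variable, such as the last on-treatment score, is defined there or in Appendix B, where the on-treatment analysis is one of four supportive mRSS analyses.

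**Data available from stoppers.** Protocol 10.3.4 gives patients who stop permanently a premature end-of-treatment (EOT) visit, with mRSS, and asks them to attend the remaining visits. SAP Table 3 (2.5.4) assigns Days 127 to 207 to Week 24, with target Day 169.

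**Planning figures (SAP 1.3, Protocol 11.1).** 10% of patients stop; the effect is 4 points under full adherence and 3.6 points in all randomized patients; SD 7; 47 per group; one-sided alpha 5%.

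**The concern.** The documents do not define the estimand strategies, so I take the terms in their usual sense. Under a while-on-treatment strategy the outcome is the response up to stopping, however early that is, and nothing after stopping has to be predicted. Under a hypothetical strategy the outcome is what would have been seen at Week 24 had the patient continued.

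The SAP names the first and specifies an analysis that, for early stoppers, leads to the second. Dropping the later values restricts the input data, but the contrast is still the LSmeans difference at Week 24 for every treated patient. At stake is how one secondary result is described: a report that follows the SAP could present an effect under continued treatment as the effect during the treatment patients actually took.

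**Working it through.** **1. The plan's own figures.** Dilution: 4 × (1 − 0.10) = 3.6. Standard error of the difference: 7 × √(2/47) = 1.44. Power: Φ(3.6/1.44 − 1.645) = 0.80. Both stated figures reproduce. The plan therefore already separates a full-adherence effect (4) from an all-randomized effect (3.6).

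**2. What the on-treatment MMRM does, by time of stopping.**

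- *Last on-treatment value before Day 127* (Day 127 = 7 × 18 + 1, that is, Week 18). The patient has no Week 24 value. Under missing at random, the model infers one from the patient's earlier scores and from patients still on treatment in the same arm. This is the response had treatment continued.
- *Premature EOT visit on or after Day 127 and within 7 days of the last dose.* The score is on-treatment and lies in the Week 24 window, so it enters directly as Week 24. For these patients the analysis does use the response up to stopping.

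The estimator is thus a hybrid, and it is hypothetical for everyone who stops early.

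**3. Illustrative size.** Let d be the proportion stopping (same proportion and timing in both arms, unrelated to outcome), E(24) the full-adherence effect, and E(s) the effect at stopping week s.

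- While-on-treatment = (1 − d) × E(24) + d × E(s)
- Gap to full adherence = d × [E(24) − E(s)]

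The documents give no onset curve. Assume linear build-up, E(s) = 4 × s/24: 0.67 at Week 4, 1.33 at Week 8, 2.00 at Week 12, 3.33 at Week 20. Assume for treatment policy that stoppers lose all benefit, as the 3.6 implies.

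| d | Stop Week 4 | Stop Week 8 | Stop Week 12 | Treatment policy | Full adherence |
|---|---|---|---|---|---|
| 10% | 3.67 | 3.73 | 3.80 | 3.60 | 4.0 |
| 20% | 3.33 | 3.47 | 3.60 | 3.20 | 4.0 |
| 30% | 3.00 | 3.20 | 3.40 | 2.80 | 4.0 |

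At 10% with stopping at Week 20: 0.9 × 4 + 0.1 × 3.33 = 3.93, a gap of 0.07. Week 20 is Day 141, inside the Week 24 window, so even that gap closes for stoppers whose EOT visit falls within 7 days of the last dose.

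The sign of the gap is the sign of E(24) − E(s). It is zero if the effect has reached its plateau before stopping, and negative if the effect wanes by Week 24.

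**4. Check that the MMRM targets full adherence for early stoppers.** Simulation with 400,000 patients per arm, visits at Weeks 4, 8, 12 and 24, and stopping after Week 4, 8 or 12. Assumed: linear effect to 4 points, placebo change of −2 points at Week 24, SDs 4, 5, 5.8 and 7, correlation 0.75 per visit step. Analysis windows were not modelled. Size of the benefit:

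| Stopping (active / placebo) | True full adherence | On-treatment MMRM | While-on-treatment |
|---|---|---|---|
| 10% / 10%, random | 3.98 | 3.98 | 3.72 |
| 8.4% / 10.4%, depends on last mRSS | 4.00 | 3.99 | 3.81 |
| 20% / 20%, random | 4.00 | 4.01 | 3.46 |
| 20% / 10%, random | 4.00 | 3.99 | 3.32 |
| 8.3% / 19.6%, depends on last mRSS | 3.98 | 3.97 | 3.98 |

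The MMRM follows the full-adherence effect throughout. The last row shows that unequal stopping can remove the gap even with a linear onset.

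**5. Scale.** At 10% stopping at Weeks 4 to 12 the gap is 0.20 to 0.33 points, or 0.20/1.44 = 14% to 0.33/1.44 = 23% of one standard error. It comes from about 0.10 × 47 ≈ 5 patients per arm.

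**The case against.** The strongest reply is that little is hidden and little depends on this. SAP 2.4.4.1.3 states the variable, model, data cut and population, and the preceding primary-analysis section states the missing-at-random assumption. The output is well specified; one label and one loosely worded sentence are at fault. That sentence could even be read as describing the effect under adherence. The Week 24 window also means that a purely hypothetical label would not be exact. All of this stands, and it limits the point to a correction of wording.

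It does not remove the mismatch. The label sentence is explicit, and for anyone who stops before Day 127 the specified contrast is not a while-on-treatment quantity. The control-based imputation in 2.4.4.1.7 does not help: the SAP offers it as a robustness check on the primary analysis, and it neither relabels nor estimates this estimand.

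A reader might infer two stronger things. One is that the conclusion of the main supportive analysis would be wrong. The documents do not support this: the SAP calls the analysis secondary, Appendix B lists it with three others, no decision rule uses it, and the illustrative gap is well under one standard error. The other is that the planned figure is necessarily the more favourable. That requires a benefit still growing at Week 24, and no section gives the onset shape.

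**Conclusion.** The label and the estimator in SAP 2.4.4.1.3 do not match. For patients who stop before Day 127 the analysis essentially targets a hypothetical strategy; from Day 127 on, a premature EOT score may count directly as Week 24. This follows from the text and needs no numerical assumption.

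The consequence is minor. The primary treatment-policy analysis, sample size and type I error are unaffected. The illustrative gap of 0.20 to 0.33 points at the planned 10% rests on linear onset, equal stopping in both arms and stopping at Weeks 4 to 12. It grows with more stopping, shrinks with later stopping, disappears with a plateau and reverses with waning.

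**What to change.** Choose one in SAP 2.4.4.1.3:

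1. **Relabel.** Call the estimand a hypothetical strategy (the effect had patients remained on treatment to Week 24), state the missing-at-random assumption in that section, and say how premature EOT scores inside the Day 127 to 207 window are treated. Revise the explanatory sentence to match. Cost: SAP wording only.
2. **Keep the label and change the analysis.** Define the variable as change from baseline to the last on-treatment mRSS, and estimate it with an ANCOVA adjusted for randomization stratum and baseline mRSS. Cost: one additional model on data already collected.

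If both quantities are of interest, do both under separate names.
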